**A pre-consultation compassion video to reduce anxiety among patients referred
to a cancer center: a randomized control trial**

Protocol

4/18/21

Participants

We will enroll adult patients scheduled for an initial cancer consultation at MD Anderson Cancer Center at Cooper. Inclusion criteria include: 1) age \geq 18 years; 2) scheduled for an initial cancer consultation. We will exclude patients who do not have an active email address or are medically unable to complete the research questionnaire at the time of the initial cancer consultation.

Intervention, randomization and masking

All new adult patients scheduled for an initial cancer consultation at MD Anderson Cancer Center at Cooper will be randomized to receive an email containing a link for either the “standard introduction video” or the “enhanced compassion video.” Subjects will receive either an information only standard introduction video (76 seconds) or an enhanced compassion video (107 seconds). The two videos featured the same oncologist (i.e. Medical Director of the cancer center) and are identical except the enhanced compassion video contains five additional compassion-focused statements. An independent statistician will generate the group assignment sequence using a parallel design, 1:1 simple randomization schedule. The randomization assignments will be kept in a sequential list and maintained in the scheduling operator office. At the time of scheduling an initial consultation, appointment operators will identify the next assignment in the series, which will be labeled either “Video A” or “Video B.” The operators will then send the appropriate email containing a link to a website for the matching video. The independent statistician will maintain the code link for the videos. When the patients arrive to the Cancer Center waiting room for his/her initial cancer consultation they will be approached by research staff to obtain written informed consent to complete the research questionnaire and for use of data.

Outcome measures

The primary outcome measure will be anxiety severity on arrival to the cancer center for the initial consultation. As part of the research questionnaire patients will be asked to complete the Hospital Anxiety and Depression scale (HADS). The HADS Depression score will be analyzed as a secondary outcome.

Statistical analysis:

We will use the Wilcoxon rank-sum test to test for a difference in the HADS anxiety scale between the two video groups and quantile regression to report the median difference with 95% CI. For our secondary outcome measure we will repeat the same analyses using the HADS depression scale in place of the HADS anxiety scale. We will perform all analyses using intention to treat principle.

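### The assignment list sits in the office of the operators who send the video links, and no described step hides later entries or logs the patient before the label is seen

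*Combined protocol and SAP*

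**What the plan says.** All of the allocation procedure is in the section on intervention, randomization and masking.

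- Generation: "An independent statistician will generate the group assignment sequence using a parallel design, 1:1 simple randomization schedule".
- Storage: "The randomization assignments will be kept in a sequential list and maintained in the scheduling operator office".
- Use: when a consultation is booked, "appointment operators will identify the next assignment in the series", which reads Video A or Video B.
- Delivery: "The operators will then send the appropriate email containing a link to a website for the matching video".
- Code: "The independent statistician will maintain the code link for the videos".
- Who is randomized: "All new adult patients scheduled for an initial cancer consultation" at the center.
- Consent: on arrival, "they will be approached by research staff to obtain written informed consent to complete the research questionnaire".

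The Participants section excludes patients without a working email address. It does not say who checks this or when. Under Statistical analysis, the primary comparison is a rank-sum test of HADS anxiety between the two groups, by intention to treat, with no covariate adjustment described.

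**The concern.** Concealment means that whoever enters a patient cannot know the assignment until the patient is irrevocably in the trial. Here the list is in the operators' workplace. The same staff read the label and deliver the intervention, and the plan mentions no envelope, central or electronic release, or log made before the label is read.

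Two selection routes stay open. One is the order in which patients are matched to lines of the list. The other is how the email exclusion is applied, if it can be decided after the label is visible.

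The primary test is unadjusted, and the only anxiety measurement described is the one on arrival, after the video was sent. The comparison therefore rests on assignment being independent of how anxious patients already were. The plan describes nothing that would detect or correct a departure from that.

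**Working it through.** **What each described safeguard covers**

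| Safeguard in the plan | Protects against | Leaves open |
|---|---|---|
| Simple 1:1 sequence from an independent statistician | Guessing the next entry from past ones | Reading the next entries directly |
| A/B labels, code held by the statistician | Knowing what a label means | Seeing which label comes next; learning the code from the links, since the videos differ by 107 − 76 = 31 seconds and by five statements |
| All new adult patients randomized | Picking who enters | Order of entry; when the email exclusion is judged |
| Consent by research staff, HADS completed by the patient | Operator influence on consent and outcome | Allocation itself |
| Intention to treat | A wrong link sent against a standing assignment | A patient entered out of order or left out before entry |

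No row supplies the missing step.

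**Size, by assumption.** The plan gives no sample size, alpha or steering rate to reproduce. Assumed: N = 200, two-sided alpha 0.05, no true effect, and perceived distress and HADS anxiety both standard normal with correlation r. A patient in the top quarter of perceived distress whose next line is the standard video is, with probability q, given the next compassion line instead. The skipped line takes its place.

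Hand calculation:

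- Mean perceived distress in the top quarter = 0.3178 / 0.25 = 1.271 SD.
- Each swap moves such a patient one way and an average patient the other, so the arm difference (compassion minus standard) ≈ 4 × s × 1.271 × r, where s is the share of swap events.
- Standard error = 2/√200 = 0.1414 SD; rank-sum efficiency factor √(3/π) = 0.977.
- Example, s = 0.071 and r = 0.5: difference = 4 × 0.071 × 1.271 × 0.5 = 0.180 SD. Standardized: 0.180 / 0.1414 × 0.977 ≈ 1.25. Rejection probability ≈ P(Z > 0.71) + P(Z > 3.21) ≈ 23.8% + 0.1% ≈ 24%.

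| Patients changing arm (swap events) | r | Difference, SD | Error rate, hand | Error rate, simulated |
|---|---|---|---|---|
| 6.2% (3.3%) | 0.1 | 0.017 | 5.2% | 5.0% |
| 6.2% (3.3%) | 0.3 | 0.050 | 6.4% | 6.2% |
| 6.2% (3.3%) | 0.5 | 0.084 | 8.9% | 8.9% |
| 12.4% (7.1%) | 0.1 | 0.036 | 5.7% | 5.3% |
| 12.4% (7.1%) | 0.3 | 0.108 | 11.6% | 11.7% |
| 12.4% (7.1%) | 0.5 | 0.180 | 24% | 25.1% |

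Simulated rates use 3,000 to 4,000 runs per setting (Monte Carlo error about 0.3 to 0.8 percentage points). With no steering the simulated rate is 5.1% to 5.4%.

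**Direction.** The difference is positive: the compassion arm becomes more anxious. In simulation at 12.4% changed, significant results split 24.7% for the standard video against 0.1% for the compassion video at r = 0.5, and 11.6% against 0.3% at r = 0.3.

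**Other cases, N = 200**

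- Email exclusion applied after seeing the label, to the same kind of patient: 3.2% left out gives 0.025 SD and 4.9% (r = 0.3), or 0.041 SD and 6.0% (r = 0.5); 6.6% left out gives 0.053 SD and 6.7%, or 0.088 SD and 9.3%.
- Mixed-direction swaps: 4.5% to 5.3%.
- Wrong link sent but analyzed as assigned: 4.4% to 5.3%. The cost is dilution: with 6.2% of patients sent the wrong link, all in the standard arm, an assumed difference of 0.40 SD becomes 0.40 × (1 − 0.062/0.5) = 0.35 SD.

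**Dependence on N**, at the higher steering rate: 7.9% (r = 0.3) and 13.7% (r = 0.5) for 100 patients; 19.0% and 43.1% for 400.

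**The case against.** A consistent one-way bias needs several things at once. An operator must learn the code, form an impression of the patient's distress, read ahead or skip lines despite the next-in-series rule, and steer the same way each time. The documents show none of these. They do not say that operators open links or discuss distress with patients, or that the email exclusion is theirs to apply. Naming the office where a list is kept does not establish who can see its later entries, and a short protocol may simply omit a concealment step that exists. All of this stands, and it limits the point to an unprotected risk.

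The illustration is also open to challenge. A correlation of 0.3 to 0.5 between a scheduling impression and self-reported anxiety has no support in the documents, and at 0.1 the error rate is essentially nominal. That stands too.

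A reader might infer from a raised error rate that the trial is prone to falsely claiming that the compassion video works. The modeled direction does not support that. It pushes the chance of a false claim of benefit below its nominal 2.5% and would instead hide a real benefit. Only steering the other way would create a false one, and the documents give no reason to expect either.

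What the objection does not remove is that the plan states a concrete procedure, and that procedure puts the list with the people who use it.

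**Conclusion.** The point holds as a gap in allocation concealment. The list is kept where the operators work, the same operators read it and send the links, and nothing described hides later lines or fixes the patient's entry first. The A/B coding is a real masking step, but it hides what a label means and not which label comes next.

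A reader might go further and conclude that allocation was biased or that operators knew which video each patient would get. The documents support neither.

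The size is conditional on assumed values for N, correlation, steering rate and direction. It runs from no material effect (weak correlation, few patients changed, or mixed directions) to an error rate of about 25% for 200 patients when 12% change arm at correlation 0.5, with the sign set by the direction of steering. The change is worth making because it is cheap, not because harm has been shown.

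**What to change.** Keep the statistician's 1:1 simple sequence, but hold it outside the scheduling office, for example in a simple electronic randomizer. Release one assignment per patient, only after the patient's identifier and email address have been logged and time-stamped, so that the email exclusion is settled first. Check the emails sent against the sequence, and analyze each patient by the released assignment. If later entries are already hidden in practice, the protocol should say how, and state that the patient is logged first.

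Cost: one protocol paragraph, set-up of the randomizer and a few extra fields per patient. Sample size, visits and the planned tests do not change.

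### Should the primary HADS anxiety comparison be adjusted for age, clinic and appointment wait, instead of resting on an unadjusted rank test after simple randomisation?

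*Combined protocol and SAP*

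**What the plan says.** Under Intervention, randomization and masking, the sequence is generated "using a parallel design, 1:1 simple randomization schedule", with no blocking or strata. It is applied at booking: "At the time of scheduling an initial consultation, appointment operators will identify the next assignment in the series". Under Outcome measures, the endpoint is a single measurement: "The primary outcome measure will be anxiety severity on arrival to the cancer center for the initial consultation". No HADS before the video is described.

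The Statistical analysis section has two parts for the primary outcome. The test is given as "We will use the Wilcoxon rank-sum test to test for a difference in the HADS anxiety scale between the two video groups", and the estimate comes from "quantile regression to report the median difference with 95% CI". HADS depression gets the same treatment, and the section ends: "We will perform all analyses using intention to treat principle". No covariate, adjusted model or supportive analysis is named for either outcome.

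On possible covariates the document says little. Age enters through the adult criterion under Participants. The wait could be worked out from booking and visit dates. Clinic or tumour service is not mentioned as a variable; the text names one center.

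**The concern.** Neither the design nor the analysis uses prognostic information. Simple randomisation does not force balance on anything, a two-sample rank test cannot take covariates, and there is no baseline score to absorb differences between patients. Age and the booked wait could plausibly be had without another visit. The wait also sets how long before the questionnaire the video link was sent, so it bears on this intervention in particular.

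Two things would be at stake. Any variation in anxiety that these variables explain stays in the error term and costs power. And if the arms happen to differ on one of them, the observed difference between arms carries part of that imbalance, while an adjustment chosen after seeing it would be post hoc.

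**Working it through.** **Inputs.** The documents give no sample size, alpha, power, effect size or standard deviation, so there is no figure of the plan's own to reproduce. Assumed for illustration: two-sided alpha 0.05, 80% power, a standardised difference of 0.4, and R-squared from 0.02 to 0.30. The simulation used 4,000 runs per setting, 200 patients, simple randomisation, a rounded score from 0 to 21 with SD about 4, and three prognostic covariates. It compared the Wilcoxon test with a covariate-adjusted analysis of ranks.

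**Step 1: validity.** With no true effect, the Wilcoxon test rejected in 4.4% to 5.2% of runs over the five R-squared values. Simulation error around 5% is sqrt(0.05 × 0.95 / 4000) = 0.34 percentage points, so this range is consistent with the nominal level. The reference distribution of the test already allows for chance imbalance.

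**Step 2: precision.** For an adjusted mean difference the standard error is multiplied by sqrt(1 − R²), and the equivalent gain in sample size is 1/(1 − R²) − 1. The number per arm is 2 × (1.960 + 0.842)² × (1 − R²) / 0.4² = 98.1 × (1 − R²), rounded up. Unadjusted, that is 99.

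| R² | Equivalent extra patients | SE factor | n per arm (unadjusted 99) | Simulated power, Wilcoxon to adjusted ranks |
|---|---|---|---|---|
| 0.02 | 2.0% | 0.990 | 97 | 77.9% to 78.4% |
| 0.05 | 5.3% | 0.975 | 94 | 79.0% to 80.1% |
| 0.10 | 11.1% | 0.949 | 89 | 78.3% to 81.3% |
| 0.20 | 25.0% | 0.894 | 79 | 78.0% to 86.2% |
| 0.30 | 42.9% | 0.837 | 69 | 77.2% to 88.5% |

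The gain is 0.5 to 1.1 points at R² of 0.02 to 0.05, about 3 points at 0.10, and about 8 points at 0.20.

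**Step 3: chance imbalance.** The standardised difference in a covariate has standard error 2/sqrt(N). The probability that it exceeds 0.2 in either direction is 32% at N = 100, 16% at N = 200 and 4.6% at N = 400. For at least one of three independent covariates it is 68%, 40% and 13%. Such imbalances are common in small trials, but their effect depends on R². An imbalance of 0.2 shifts the estimate by 0.2 × sqrt(R²) outcome SDs. At R² = 0.05 that is 0.2 × 0.224 = 0.045 SD, against a standard error of 2/sqrt(200) = 0.141 SD at N = 200. The shift is therefore about a third of one standard error.

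**Step 4: the candidate covariates.** Age is implied by eligibility. The wait is a baseline variable only if counted to the date first booked; counted to the visit attended, it can change after assignment through rescheduling. Clinic has no support in the text: "All new adult patients scheduled for an initial cancer consultation at MD Anderson Cancer Center at Cooper will be randomized" names a single center and no service within it.

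**Step 5: the alternative.** A proportional-odds model with covariates estimates a conditional odds ratio, which differs from the unadjusted one even when the arms are perfectly balanced. The standard-error factors in step 2 belong to a mean difference and do not carry over to that odds ratio. Putting such a model first would also displace the planned median difference as the main effect measure.

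**The case for a change.** The best case for a change is that adjustment costs little and did not lose power in any setting simulated, even at R² = 0.02. The documents state no sample size, so a small trial with frequent imbalance cannot be ruled out. A sentence written before unblinding would also settle which adjustment counts. In addition, patients are assigned at booking but consent on arrival, so those analysed are a subset formed after randomisation, and booking-time covariates might offset part of any selection.

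Much of this stands. The direction of the gain is right, and a pre-specified supportive analysis on age and the originally booked wait would be good practice. It still does not amount to a needed change. The gain depends entirely on an R² that the documents do not supply, and without a baseline HADS the covariate most likely to make it large is absent. Selection between booking and arrival is a separate question about missing outcomes, which adjustment for age and wait would at best partly address. The quantile regression already in the plan can take covariates, so analysts who want an adjusted estimate have a ready route, provided they report it as conditional on those covariates.

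**Conclusion.** The plan is valid as written, and no change follows. An unadjusted rank test with a median difference is a simple, defensible analysis of a bounded ordinal score, and it keeps its error rate under simple randomisation. What is given up is efficiency of unknown and probably small size: about 0.5 to 1.1 points of power if the covariates explain 2% to 5% of the variance, and 8 points or more only if they explain about 20% or more. These figures rest on an assumed N of 200, a standardised difference of 0.4 and assumed R² values.

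Replacing the primary analysis would exchange the planned median difference for another estimand, a choice on which competent statisticians would differ. Adding a supportive adjusted analysis is a reasonable option for the analysts, but the trial's primary result and conclusion would still rest on the unadjusted comparison.
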